Patients who relapse (< 30×10 ⁹ /L) after eltrombopag discontinuation before Week 52	Re-initiate treatment with eltrombopag with a starting dose of 50 mg/day till Week 52 and discontinue from study at Week 52	

Treatment in the control arm consists of 1-3 cycles of high-dose dexamethasone administered orally at a dose of 40 mg QD for 4 consecutive days at 4 weeks intervals (dexamethasone can also be given at 14 to 28 days intervals if needed according to current ITP guidelines). If the platelet counts are $> 150 \times 10^{9}$ /L no further course of dexamethasone will be given. Patients will be treated up to 12 weeks (3 months) during the treatment period with dexamethasone. Patients who reach platelet counts $\ge 30 \times 10^{9}$ /L and maintain counts $\ge 30 \times 10^{9}$ /L after 1-3 cycles of high-dose dexamethasone treatment will be eligible for treatment discontinuation. Patients with platelet counts $< 30 \times 10^{9}$ /L after 3 cycles of dexamethasone treatment will be offered a course of eltrombopag treatment within the study and will discontinue the study after completion of treatment with eltrombopag at Week 52 (Table 6-2).

Table 6-2Dexamethasone dosing guidance for patients not meeting criteria for
sustained remission

Platelet Level	Dose Guidance
Patients with platelet count < 30×10 ⁹ /L after 3 cycles with dexamethasone	Initiate treatment with eltrombopag with a starting dose of 50 mg/day and continue treatment with eltrombopag till Week 52 after study start and discontinue from study at Week 52
Patients who relapse (platelet count < 30×10 ⁹ /L) after dexamethasone discontinuation before Week 52	Initiate treatment with eltrombopag with a starting dose of 50 mg/day till Week 52 after study start and discontinue from study at Week 52

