6.1.4 Treatment duration

Arm A: The treatment duration for all patients in Arm A (eltrombopag QD for 26 weeks + high-dose dexamethasone QD for 4 consecutive days starting at day 1 and limited to 1 cycle) will be 26 weeks (6 months) including 6 weeks tapering period. All patients who discontinue study treatment as per study design with platelet counts $\geq 30 \times 10^{9}$ /L in the absence of bleeding or use of any rescue therapy will be followed for response assessments till Week 52 after study start. Patients who relapse after eltrombopag discontinuation before Week 52 will reinitiate treatment with eltrombopag till Week 52 and will discontinue from study at Week 52. Patients with platelet counts < 30×10^{9} /L after 26 weeks of treatment with eltrombopag will continue treatment as summarized in Table 6-1 and discontinue from study at Week 52.

Arm B: The maximum duration of treatment with dexamethasone for all patients in Arm B will be 12 weeks. All patients who discontinue study treatment as per study design with platelet counts $\geq 30 \times 10^9/L$ in the absence of bleeding or use of any rescue therapy will be followed for response assessments till Week 52. Patients who relapse (platelet count $< 30 \times 10^9/L$) after dexamethasone discontinuation before Week 52 will be treated with eltrombopag as summarized in Table 6-2 and discontinue the study at Week 52. Patients with platelet count $< 30 \times 10^9/L$ after 3 cycles with dexamethasone will initiate treatment with eltrombopag and discontinue the study at Week 52.

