12.5.2 Safety endpoints

Safety summary tables include only data from the period from first treatment until 30 days after the patient has stopped study participation (defined as last visit).

Adverse events

All information obtained on AEs will be displayed by treatment group and subject.

The number (and percentage) of subjects with treatment-emergent AEs (events started after the first dose of study medication or events present prior to start of treatment but increased in severity based on preferred term) will be summarized in the following ways:

- by treatment, primary system organ class and preferred term.
- by treatment, primary system organ class, preferred term and maximum severity.
- by treatment, Standardized MedDRA Query (SMQ) and preferred term

Separate summaries will be provided for study medication related AEs, death, SAEs, other significant AEs leading to discontinuation and adverse events leading to dose adjustment.

The number (and proportion) of subjects with AEs of special interest (i.e. thromboembolic/thrombotic complications, hepatobiliary laboratory abnormalities, bleeding,

bone marrow reticulin formation and bone marrow fibrosis, and ocular changes) will be summarized by treatment.

A subject with multiple AEs within a primary system organ class is only counted once towards the total of the primary system organ class.

All information obtained on AEs will be displayed by patient. Summary tables for AEs will include only AEs that started or worsened during the on-treatment period, the **treatment-emergent** AEs (TEAEs).

The incidence of TEAEs will be summarized by system organ class (SOC) and or preferred term, severity based on the CTCAE grades, type of AE and relation to study treatment.

Serious adverse events, AEs leading to discontinuation, AEs leading to dose adjustment and AESI which includes bleeding events during the on-treatment period will be tabulated.

The incidence of AESIs will be summarized by SOC and Preferred Term (PT).

All deaths (until 30 days after the patient has stopped study participation defined as last visit.s) will be summarized.

All AEs, deaths and SAEs will be listed and those collected during the pre-treatment (from day of patient's informed consent to the day before first dose of study treatment) and post-treatment period will be flagged (until 30 days after the patient has stopped study participation defined as last visit)

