### 2.1.1 General definitions

**Study treatment** for patients randomized to the investigational combination treatment is eltrombopag until Week 26 in combination with 1 cycle of high-dose dexamethasone (subsequently referred to as treatment group ETB+DEX). For patients randomized to the control arm the study treatment consists of 1-3 cycles of high-dose dexamethasone (subsequently

referred to as treatment group DEX). These treatments will be called "study treatment" in the rest of the document.

When eltrombopag and/or dexame thas one will be given additionally, this is assessed as rescue or - if applicable - as concomitant medication during the data review meeting case-by-case.

The last available assessment on or before the date of start of eltrombopag is taken as "**baseline**" assessment. It is assumed that all assessments at Week 1/Day 1 are captured pre-dose on first day of eltrombopag (e.g. PROs), thus this Week 1/Day 1 is used for baseline when no screening values are available. Otherwise the screening values are considered as baseline. For all analyses on platelets the platelet count directly before pre-treatment will be used as baseline value in the pretreated patients. This is the more adequate way of taking into account the initial value at time of diagnosis and before pre-treatment for all patients

**Pre-treatment period**: from day of subject's informed consent to the day before first dose of study treatment.

**On-treatment period**: from date of first dose of study treatment to date of treatment discontinuation (including start and stop date).

**Treatment discontinuation** is the date of last study medication given as study treatment but not as rescue medication or not after after re-initiation, i.e. initial dose after failure of 1-3 DEX cycles (for details see Derivation of time point of treatment discontinuation5.1).

**Post-treatment period**: starting at day 30+1 after last dose of study treatment

The **Safety Follow-up period** specifies the observational period (30d) for which patients will be followed-up for safety events/measures.

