#### 2.8.1 Adverse events (AEs)

Only treatment-emergent AEs are included in the the safety analysis. Non-treatment emergent AEs are listed only in the Patient Data Listings (section 16.2.1 of the CSR).

Treatment-emergent adverse events (TEAE) are defined which started during the on-treatment period or increased in severity based on preferred term). The on-treatment period lasts from the

date of first dose of study treatment with eltrombopag or dexamethasone (whichever is first) to 30 days after the date of the last dose of study treatment (whichever is last).

The number (and percentage) of subjects with treatment-emergent adverse events will be summarized in the following ways:

- by treatment, primary system organ class and preferred term.
- by treatment, primary system organ class, preferred term and maximum severity (based on CTCAE grades).
- by treatment, Standardized MedDRA Query (SMQ) and preferred term

Separate summaries will be provided for study medication related AEs, death, SAEs, AEs leading to discontinuation and adverse events leading to dose adjustment.

The number (and proportion) of subjects with AEs of special interest (i.e. thromboembolic/ thrombotic complications, hepatobiliary laboratory abnormalities, bleeding, bone marrow reticulin formation and bone marrow fibrosis, and ocular changes) will be summarized by treatment.

A subject with multiple AEs within a primary system organ class is only counted once towards the total of the primary system organ class.

A subject with multiple AEs within a preferred term is only counted once towards the total of the preferred term class.

The incidence of AESIs will be summarized by SOC and Preferred Term (PT). In addition to the above mentioned analysis this analysis counts each AESI (which may occur multiple in one patient) but not only the occurrence in one patient/one SOC/one PT.

All deaths (on-treatment and post-treatment [starting at day 30+1 after last dose of eltrombopag]) will be summarized.

All AEs, deaths and SAEs will be listed and those collected during the pre-treatment (from day of patient's informed consent to the day before first dose of study treatment) and post-treatment period will be flagged.

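### Adverse events are to be shown as crude percentages over planned risk windows of about 212 days in Arm A and 34 to 114 days in Arm B, with no person-time rate and, bleeding apart, no common-window table

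*SAP*

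**What the plan says.** SAP 2.8.1 admits only treatment-emergent events to the safety tables and gives the summary measure: "The number (and percentage) of subjects with treatment-emergent adverse events will be summarized in the following ways". Protocol 12.5.2 uses the same measure: "The number (and percentage) of subjects with treatment-emergent AEs". AESIs are shown as number and proportion of patients by arm, and also as raw event counts. The SAP 2.8.1 window starts at first dose and runs "to 30 days after the date of the last dose of study treatment".

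SAP 2.1.1 defines study treatment by arm. In Arm A it "is eltrombopag until Week 26 in combination with 1 cycle of high-dose dexamethasone". For Arm B: "For patients randomized to the control arm the study treatment consists of 1-3 cycles of high-dose dexamethasone". SAP 2.1.1 and 5.1 date the end of study treatment without counting rescue use, re-initiation, or eltrombopag begun after the dexamethasone cycles have failed. Such eltrombopag therefore does not lengthen an Arm B patient's window.

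Exposure duration is summarised (SAP 2.4.1) but is not linked to adverse events. Neither document plans a person-time rate or a time-to-first-event analysis for adverse events. One related summary does use a common period: SAP 2.8.4.1 counts patients with WHO-scale bleeding up to Week 52. Deaths are summarised both on and after treatment.

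**The concern.** A crude percentage of patients with an event depends on how long each patient is watched as well as on how often events happen. Here the observation time differs between arms by design, because it follows the length of study treatment. A table of such percentages by arm cannot separate longer observation from higher toxicity, and raw AESI counts have the same weakness. Safety and tolerability of the combination is secondary objective 9, and readers will compare the two columns whether or not a test is attached.

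**Working it through.** The documents state neither a window length nor an adverse event rate, so there is no figure of theirs to reproduce. The windows below are derived from the dosing rules.

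**Inputs**
- Arm A planned duration, Protocol 6.1.4: "26 weeks (6 months) including 6 weeks tapering period", so 26 × 7 = 182 days.
- Arm B cycles, Protocol 6.1: "at a dose of 40 mg QD for 4 consecutive days at 4 weeks intervals", with intervals of 14 to 28 days also allowed.
- Arm B cap, Protocol 6.1.4: "The maximum duration of treatment with dexamethasone for all patients in Arm B will be 12 weeks", so 12 × 7 = 84 days.
- Tail, SAP 2.8.1: 30 days.

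**Planned windows (day of last dose + 30)**

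| Course | Last dose | Window (days) | Arm A window ÷ this |
|---|---|---|---|
| Arm A, full course | Day 182 | 212 | – |
| Arm B, 1 cycle | Day 4 | 34 | 212/34 = 6.24 |
| Arm B, 2 cycles every 28 days | Day 32 | 62 | 212/62 = 3.42 |
| Arm B, 3 cycles every 14 days | Day 32 | 62 | 3.42 |
| Arm B, 3 cycles every 28 days | Day 60 | 90 | 212/90 = 2.36 |
| Arm B, 12-week cap read literally | Day 84 | 114 | 212/114 = 1.86 |

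**Departures from the planned course.** Under Protocol Table 6-1, an Arm A patient still below 30 × 10⁹/L after 4 weeks at 75 mg stops eltrombopag. After 2 weeks at 50 mg that can be as early as about Day 42, a window of 42 + 30 = 72 days. An Arm A patient who relapses during tapering continues to Week 52. If the data review counts that as study treatment, the window is 364 + 30 = 394 days.

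**Illustration.** Assume the same constant hazard in both arms and a proportion p with an event by Day 90. The expected proportion by day t is 1 − (1 − p)^(t/90). The values of p are assumptions.

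| Window | p = 20% | p = 30% |
|---|---|---|
| 34 days (Arm B, 1 cycle) | 8% | 13% |
| 62 days (Arm B, 2 cycles every 28 days) | 14% | 22% |
| 90 days (Arm B, 3 cycles every 28 days) | 20% | 30% |
| 114 days (Arm B, literal cap) | 25% | 36% |
| 212 days (Arm A, full course) | 41% | 57% |
| 72 days (Arm A, early stop for non-response) | 16% | 25% |

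For example, 1 − 0.70^(212/90) = 0.568 and 1 − 0.70^(34/90) = 0.126. With no difference in hazard, a full Arm A course shows about twice the percentage of three 28-day cycles (0.409/0.200 = 2.04; 0.568/0.300 = 1.89). Patients stopping early in Arm A pull the other way.

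**The window itself is not settled.** The documents give three different ends:
- Protocol 12.5.2 opens by running safety tables to 30 days after the last visit, about 364 + 30 = 394 days in either arm for a Week 52 completer. The same section then limits adverse event tables to the on-treatment period.
- SAP 2.1.1 ends the on-treatment period at treatment discontinuation with no tail: 182 days against 4 to 60 days.
- SAP 2.8.1 adds the 30-day tail.

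SAP 2.8 refers back to Protocol 12.5.2, and SAP 4 declares no change from the protocol.

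**The case against.** The strongest reply is that the window must be settled first. If the opening sentence of Protocol 12.5.2 governed, the windows would be roughly equal and most of the problem would go. That is right as to order. But the same section later restricts adverse event tables to the on-treatment period, and SAP 2.8.1 sets an explicit last-dose rule, so the unequal window is the one the SAP as written would apply.

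Second, the results are descriptive, with about 24 patients expected. At 12 per arm the Clopper-Pearson interval is 28% to 85% for 7 of 12 and 10% to 65% for 4 of 12. This limits the practical weight of the point. It does not make unequal windows comparable.

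Third, incidence per regimen is a legitimate summary when regimens differ by design, and exposure and full listings let a careful reader see the imbalance. That stands, and is why the present tables should stay.

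Fourth, constant hazard is a strong assumption for four-day steroid pulses. Events concentrated in the first weeks would shrink the gap. This also stands: the size of the distortion is uncertain, but its direction holds for events that can still arise after the Arm B window closes.

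A reader might go further and infer that no adverse event type has a common-window summary, or that every patient falls into 212 days or 34 to 90 days. The documents support neither. Bleeding is counted to Week 52, deaths are summarised after treatment as well, the 12-week cap allows up to 114 days in Arm B, and individual windows can overlap between arms.

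**Conclusion.** The point holds, with limits. Under SAP 2.8.1 the planned full-course windows differ by a factor of about 1.9 to 6, and no planned adverse event table corrects for it except the Week 52 bleeding summary. At equal rates, events that can still occur late would look more frequent in Arm A.

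The figures of 41% to 57% against 8% to 30% rest on an assumed event rate, an equal constant hazard and completed courses. They illustrate the mechanism and do not predict this trial's results. Nor do they show that any excess seen in Arm A would be an artefact: the planned tables simply could not tell. The primary endpoint is untouched. This is a worthwhile, inexpensive reporting change that should follow reconciliation of the window.

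**What to change.** First, reconcile the adverse event window across Protocol 12.5.2 (30 days after last visit, and on-treatment only), SAP 2.1.1 (no tail) and SAP 2.8.1 (30-day tail), and state one definition.

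Then keep the present tables in SAP 2.8.1 and add, for any adverse event, SAEs and the AESIs other than bleeding:
1. Patients with a first event per 100 patient-weeks at risk, by arm. Time at risk runs from first dose to the first event or the end of the reconciled window.
2. A by-arm table over one common window, for example Day 1 to the end of Week 12. It must count all adverse events regardless of the treatment-emergent flag; otherwise events after Day 34 or Day 62 would be lost for Arm B patients given one cycle or two 28-day cycles. Show alongside it the number of Arm B patients who started eltrombopag within the window.

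The cost is two extra tables. Protocol 10.1.1 continues adverse event monitoring for at least 30 days after participation ends, and dosing dates are recorded, so no new data are needed. Two weaknesses remain: the rates assume a roughly constant hazard, and the common window may include eltrombopag exposure in Arm B. With three cycles at 14-day intervals the last dose falls on Day 32, so a switch before Week 12 is possible.

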#### 2.8.1.1 Adverse events of special interest / grouping of AEs

The AESI are identified via Novartis Case Retrieval Strategy.

#### 2.8.2 Deaths

Deaths are displayed by absolute and relative frequencies for each treatment group. Deaths are listed.

#### 2.8.3 Laboratory data

All laboratory data will be listed by treatment group, subject, and visit (including the safety follow-up visits). Values outside the center-specific normal range are flagged as "low" or "high", as well as clinically significant abnormalities and CTCAE grades, if applicable. Summary statistics will be provided by treatment group and visit. Changes are calculated from baseline to the last on-treatment value. Again (see Adverse events (AEs)2.8.1) the on-treatment period lasts from the date of first dose of study treatment with eltrombopag or dexamethasone

(whichever is first) to 30 days after the date of the last dose of study treatment (whichever is last).

Boxplots will be presented for the total study course separated by treatment group in addition.

Grading of laboratory values will be assigned programmatically as per NCI Common Terminology Criteria for Adverse Events (CTCAE) version 5.0. The calculation of CTCAE grades will be based on the observed laboratory values only, clinical assessments will not be taken into account. CTCAE Grade 0 will be assigned for all non-missing values not graded as 1 or higher. Grade 5 will not be used. For laboratory tests where grades are not defined by CTCAE v5.0, results will be categorized as low/normal/high based on laboratory normal ranges.

For laboratory tests where grades are defined by CTCAE v5.0,

- Worst post-baseline CTCAE grade (regardless of the baseline status). Each subject will be counted only once for the worst grade observed post-baseline.
- Shift tables using CTCAE v5.0 grades to compare baseline to the worst on-treatment value

For laboratory tests where grades are not defined by CTCAE v5.0,

Shift tables using the low/normal/high/ (low and high) classification to compare baseline to the worst on-treatment value.

Any significant findings in laboratory will be documented as AEs and reported as such. Laboratory data reported in the eCRF section of Adverse Events (labeled as "relevant laboratory results regarding this AE") are listed only.

#### 2.8.4 Other safety data

#### 2.8.4.1 WHO Bleeding Scale

Bleeding scales will be analyzed using the FAS.

The frequency of patients with at least one bleeding until Week 52 is calculated overall as well as for bleedings graded  $\geq 2$  and graded  $\geq 3$ .

The severity of bleedings is analyzed as frequencies regarding the worst value in the two time periods "on-treatment period" and "after on-treatment period". All bleeding events are listed including a flag in wich period they started.

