8.5.3 Other Assessments

The modified WHO (Kaufman et al 2015) Bleeding Scale (Page et al 2007) will be administered at every visit (refer Section 16.2).

9 Study discontinuation and completion

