A patient with multiple AEs within a primary SOC is only counted once towards the total of the primary SOC.

Clinical laboratory evaluations

All laboratory data will be listed by treatment group, subject, and visit/time and if normal ranges are available abnormalities will be flagged. Summary statistics will be provided by treatment and visit/time. Shift tables using the low/normal/high/ (low and high) *(or project specific)* classification will be used to compare baseline to the worst on-treatment value.

Grading of laboratory values will be assigned programmatically as per NCI Common Terminology Criteria for Adverse Events (CTCAE) version 5.0. The calculation of CTCAE grades will be based on the observed laboratory values only, clinical assessments will not be taken into account.

CTCAE Grade 0 will be assigned for all non-missing values not graded as 1 or higher. Grade 5 will not be used.

For laboratory tests where grades are not defined by CTCAE v5.0, results will be categorized as low/normal/high based on laboratory normal ranges.

The following summaries will be generated separately for hematology, and biochemistry tests:

• Listing of all laboratory data with values flagged to show the corresponding CTCAE v5.0 grades if applicable and the classifications relative to the laboratory normal ranges

For laboratory tests where grades are defined by CTCAE v5.0

• Worst post-baseline CTCAE grade (regardless of the baseline status). Each subject will be counted only once for the worst grade observed post-baseline.

• Shift tables using CTCAE v5.0 grades to compare baseline to the worst on-treatment value

For laboratory tests where grades are not defined by CTCAE v5.0,

• Shift tables using the low/normal/high/ (low and high) classification to compare baseline to the worst on-treatment value.

Other safety evaluations

Data on ECG, vital sign, height, weight and ocular findings will be summarized descriptively, listed and flagged as appropriate. Any significant findings will be documented as AEs and reported as such. Bleeding scales will be analyzed using the FAS.

The change in bleeding scale (WHO) will be provided using the worst value in the relevant time period. Listings will be provided.

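### The worst-grade-by-period bleeding table in SAP 2.8.4.1 compares periods of very unequal length between the arms and has no rule to exclude pre-dose Day 1 bleeding

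*SAP*

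**What the plan says.** SAP 2.8.4.1 plans two summaries of the WHO bleeding scale on the FAS. The first is the frequency of patients with any bleeding, bleeding of grade 2 or more, and bleeding of grade 3 or more, up to Week 52. The second concerns severity: "The severity of bleedings is analyzed as frequencies regarding the worst value in the two time periods", which it names as the on-treatment period and the period after it. Bleeding events are also listed, with a flag for the period in which they started.

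The SAP defines on-treatment in two ways. Section 2.1.1 runs it "from date of first dose of study treatment to date of treatment discontinuation (including start and stop date", and section 5.1 places that end date, for Arm B, at the last study dose of dexamethasone. Section 2.8.1, repeated for laboratory data in 2.8.3, extends it "to 30 days after the date of the last dose of study treatment (whichever is last". Section 2.8.4.1 does not choose between them.

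On Day 1, SAP 2.1.1 says: "It is assumed that all assessments at Week 1/Day 1 are captured pre-dose on first day of eltrombopag". That visit serves as baseline only when no screening value exists. "Otherwise the screening values are considered as baseline". Protocol section 12 instead uses an assessment taken pre-dose on the first treatment day as the baseline. Protocol 8.5.3 says that the scale "will be administered at every visit (refer Section 16.2", and Table 8-1 schedules it at screening and at Week 1 Day 1.

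Protocol 12.5.2 plans a further output: "The change in bleeding scale (WHO) will be provided using the worst value in the relevant time period".

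**The concern.** A worst value over a period can only rise as the period lengthens and takes in more visits. Study treatment lasts 26 weeks in Arm A and one to three four-day cycles in Arm B, so a table split by treatment status gives the two arms very different time at risk. Shown as crude frequencies, an equal bleeding risk would look like more bleeding under eltrombopag during treatment and less afterwards. The incidence and severity of bleeding is secondary objective 10, and readers will compare the percentages in the two columns directly.

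The second issue is the start of the period. Patients enter with platelets below 30 × 10⁹/L and a need for treatment, so some will be bleeding on Day 1. Both definitions of on-treatment begin on the date of first dose. A grade recorded on that date before dosing falls inside the period unless a rule removes it, and none is given.

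**Working it through.** **Plan's own durations.** Arm A: 20 weeks plus a 6-week taper = 26 weeks = 182 days, as stated in Protocol 6.1 and 6.1.4. Arm B: 3 × 28 = 84 days = 12 weeks, the stated maximum. The documents give no length for the Arm B bleeding window, so it is derived here.

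**Arm B window.** Protocol 6.1 allows one to three cycles of four days at 14- to 28-day intervals. Counting intervals start to start, the last dose falls on day (cycles − 1) × interval + 4:

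- 1 cycle: day 4
- 2 cycles: day 14 + 4 = 18 to day 28 + 4 = 32
- 3 cycles: day 28 + 4 = 32 to day 56 + 4 = 60

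**Window lengths and scheduled bleeding assessments** (visits counted from Table 8-1, Day 1 included):

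| Definition | Arm A | Arm B, 1 cycle | Arm B, 3 cycles at 28 days | Ratio A to B |
|---|---|---|---|---|
| SAP 2.1.1 | 182 days, 15 visits | 4 days, 1 visit | 60 days, 7 visits | 182/60 = 3.0 to 182/4 = 45.5 |
| SAP 2.8.1 / 2.8.3 (+30 days) | 212 days, 18 visits | 34 days, 5 visits | 90 days, 9 visits | 212/90 = 2.4 to 212/34 = 6.2 |

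If Arm B ran to the full 84 days, the SAP 2.1.1 ratio would still be 182/84 = 2.2.

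**Effect on crude frequencies.** The documents give no bleeding rate. Assume a constant rate r per week, equal in both arms, so that P(at least one bleed) = 1 − exp(−r × days/7). Take 52 weeks as 364 days. Under SAP 2.1.1 the after-treatment time is 364 − 182 = 182 days in Arm A and 364 − 60 = 304 to 364 − 4 = 360 days in Arm B.

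| r per week (assumed) | On treatment: A | On treatment: B (4 to 60 days) | After: A | After: B | First dose to Week 52, both arms |
|---|---|---|---|---|---|
| 0.5% | 12.2% | 0.3% to 4.2% | 12.2% | 19.5% to 22.7% | 22.9% |
| 1% | 22.9% | 0.6% to 8.2% | 22.9% | 35.2% to 40.2% | 40.5% |
| 2% | 40.5% | 1.1% to 15.8% | 40.5% | 58.0% to 64.2% | 64.7% |
| 5% | 72.7% | 2.8% to 34.9% | 72.7% | 88.6% to 92.4% | 92.6% |

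With the 30-day extension and r = 2%, the on-treatment figures are 45.4% in Arm A against 9.3% to 22.7% in Arm B. The gap is smaller but in the same direction.

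**A true benefit.** Let Arm A's rate be half of Arm B's: 1% against 2% per week. The on-treatment table still shows more bleeding in Arm A, 22.9% against 1.1% to 15.8%. The common window to Week 52 shows the benefit, 40.5% against 64.7%.

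**Day 1 carry-over.** If a share π of each arm is already bleeding at Day 1 and is counted, P becomes π + (1 − π) × P, and any difference between the arms is multiplied by (1 − π). For the 24.1-point Week 52 difference above (64.65 − 40.55):

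- π = 20%: 24.1 × 0.8 = 19.3 points
- π = 40%: 24.1 × 0.6 = 14.5 points
- π = 60%: 24.1 × 0.4 = 9.6 points

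These shares are assumptions. Randomisation should make π similar in the two arms, so the effect is dilution and favours neither.

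**The case against.** The strongest reply is that SAP 2.8.4.1 also reports any, grade 2 or higher, and grade 3 or higher bleeding up to Week 52, which covers incidence and severity over one window for both arms. That stands. A reader might infer that the bleeding analysis cannot show a treatment effect at all. The documents do not support this, because the Week 52 frequency is unaffected by the unequal lengths. What it lacks is a stated start: the scale is recorded at screening and on Day 1, so earlier bleeding could be counted.

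A reader might also infer that Day 1 bleeding is certain to be counted as on-treatment. That follows from the dates, but the SAP does not say it. The listing flags events by onset, and SAP 5.2.4 imputes a missing start day of bleeding, so onset dates are held. If the table used onset, bleeding that began before Day 1 would drop out. The rule is missing, which is not the same as wrong. Likewise, a one-cycle Arm B patient has the pre-dose Day 1 visit as the only scheduled assessment under SAP 2.1.1 alone. With the 30-day extension there are four more.

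It is tempting to say that the protocol's change in bleeding scale was dropped. SAP 2.8 refers to protocol section 12.5.2 for the safety analysis, so the change is largely covered by reference, although 2.8.4.1 does not spell it out.

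Bleeding is also recorded as adverse events, and the adverse-event tables count only events that started or worsened on treatment. That deals with pre-dose bleeding there, but those tables use the last-dose-plus-30-days period, so the unequal lengths remain.

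Finally, about 24 patients are expected and everything is descriptive. That limits the consequence, but it does not make the two columns comparable.

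**Conclusion.** The point holds for the worst-grade-by-period table. Its on-treatment period is about 3 to 45 times longer in Arm A under SAP 2.1.1 (2.2 times if Arm B runs to 84 days), or 2.4 to 6.2 times longer under SAP 2.8.1 and 2.8.3, and 2.8.4.1 does not say which applies. Followed exactly, the plan makes equal bleeding risk look worse for Arm A on treatment and better afterwards, at every assumed rate from 0.5% to 5% per week. The lack of a rule on pre-dose bleeding is a secondary gap. It touches both this table and the start of the Week 52 frequency, and would mainly dilute a difference.

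The window lengths assume planned durations. Early stopping shortens Arm A's window, and Table 6-1 has patients who relapse during the taper continue eltrombopag to Week 52. The percentages are illustrations under a constant assumed rate and do not predict this trial's results.

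**What to change.** In SAP 2.8.4.1:

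1. Take the pre-dose Day 1 WHO grade as the bleeding-scale baseline, in line with Protocol section 12, and add a matching exception to the baseline rule in SAP 2.1.1. Count only bleeding that starts or worsens after first dose.
2. Report worst post-baseline grade, and change or shift from baseline, over a window common to both arms: first dose to Week 52, optionally split into a few calendar intervals such as Weeks 1–26 and 27–52. Add a note that Arm B time after failure may include eltrombopag.
3. If the on-treatment and after-treatment split is kept, name one on-treatment definition and add patient-time rates.
4. Start the until-Week-52 frequency after first dose.

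The scale is already collected at every visit, so the cost is SAP wording and one or two extra or re-programmed descriptive tables. They will be sparse with about 12 patients per arm, which is a reason to keep the number of intervals small. The SAP history records that version 3.0 was agreed before database lock and signed shortly after it, so tables added later should be labelled as such.
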